1.0 Objectives / Specific Aims

- Objective: Study the safety and efficacy of uniform nonequilibrium, nonthermal atmospheric pressure plasma (NTAP)/cold atmospheric plasma device (CAP) in the treatment of molluscum contagiosum and vercurra (warts) in children 4-21 years.
- Aim:
 - Measure the changes in size, pain and appearance of verrucae and molluscum after 4, 8 and 12 weeks.
 - Evaluate the safety profile and patient tolerability of the treatment by analyzing potential side effects and pain levels, or lack thereof, with each treatment.
- Hypothesis: NTAP will be an equally efficient and painless alternative to cryotherapy for the treatment of molluscum and warts.

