3.0 Intervention to be studied (if applicable)

We will utilize a floating electrode-dielectric barrier device (FE-DBD) Cold atmospheric plasma (CAP) device on molluscum and warts in children and adolescents 4-21 years (Figure 1). Children and adolescents are targeted because they are the population most affected by painful standard of care therapy. The study will continue until at least 68 warts and 68 molluscum are treated. Each patient will not have more lesions treated than SOC recommendations. Half the lesions will be treated with plasma and the other half with standard of care being cryotherapy for warts and cantharidin for molluscum. A single patient must have minimum of 1 clinically diagnosed lesion treated and maximum of 20 treated. Lesions with a clinical impression of warts or molluscum will be selected. Selection of treatment type (control vs NTAP) will be randomly selected. Lesions

Page 3 of 13

The treatment device in this study generates cold atmospheric plasma. Cold atmospheric plasma has certain properties of plasma, such as ionized gas molecules. To create plasma, a pulse generator supplying 20-kV pulse of 20-ns pulse width at 200 Hz (FPG10-01NM10, FID GmbH, Burbach, Germany) to a 5-mm diameter quartz-covered copper electrode of 10-cm length and 1-mm quartz thickness (5). These nanosecond pulse parameters were chosen to provide sufficient treatment dose at the high level of plasma uniformity required to avoid any tissue damage. We treated the lesions for approximately 1 to 2 minutes each, moving the electrode gently over the treatment area.

After the study treatments are completed, we will analyze the data to see if the treatment was safe and effective.

Non-significant risk device statement (6-19) (Figure 1)

- We are proposing a clinical trial floating electrode-dielectric barrier device (FE-DBD) a Cold Atmospheric Plasma (CAP) device.
- While novel to the medical field and especially to dermatology, there are already a number of publications regarding its use on human skin in adults (20-26) and children (29).
- CAP devices utilize noble gases (such as helium) to deliver plasma state matter to the skin. As
 its name implies, the generated plasma stream is of near skin temperature and it exists on
 normal atmospheric pressure. During the generation of the plasma there is no electric contact
 with the patient. The treatment does not increase skin surface temperature and the used helium

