6.0 Number of Subjects

Total of 150 would be required (half control, half NTP) to achieve 80% power with an alpha of

.05.

Calculation:

- Assumption for Probabilities for the Null hypotheses is P1=P2=P3=1, hence P1 = .333333, P2 = .333333, P3 = .333333 and P1+P2+P3 = 1.0 or that each proportion has an equal chance.
- Assumption for Probabilities for Alternative Hypothesis is taken from Provided NTP paper where P1=9/17 (Full Resolution = .53), P2=3/17=.18 (Some Improvement), and P3=5/17=.29 (no improvement).

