- Patient will return to the office for a 4-week standard of care follow-up. Study cessation or additional treatment will be determined by the provider assessment of lesion clearance. If lesion persist another treatment will occur. No greater than 3 treatments will be performed.
- This study will be single blinded, meaning the study team member accessing the results will
 not know which lesions were treated with what therapy. Assessment of clearance will be based
 off of clinical examination and images. The team will record any additional clinical feature
 that may arise during the analyses.

11. Data Management

- Continuous data will be summarized using descriptive statistics (number of values, means, standard deviation, median, minimum and maximum). Categorical data will be summarized using frequency tables (frequencies and percent).
- Chi-square analysis comparing the proportions of successes (equal chance outcomes).
- Coded dermoscopic and clinical photographs may be obtained for further analyses after each visit. Files with patient images will be stored in a secure departmental drive that will only be accessible to study team members by their unique MUSC ID and password.
- All subject medical record information and data collection will be coded and stored on an MUSC Box drive only accessible to study team members and will be protected by two-factor authentication. The linking document between ID and PHI will be maintained separately from the study data in a separate encrypted folder.

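### Harms are to be reported as bare frequencies and percents, so zero events would appear as 0% with no statement of which harm rates the trial can exclude

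*Combined protocol and SAP*

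**What the plan says.** Safety is a stated purpose of the trial. Section 1.0 names it in the objective and in the second aim, and Section 3.0 says that after the study treatments "we will analyze the data to see if the treatment was safe and effective".

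The Study Endpoints section lists local signs, scarring and dyspigmentation among them, each graded 0 to 3. Section 15.0 names blistering, scarring, pigmentary alteration and nail change as harms that could occur and will be monitored.

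The analysis of all this is in Section 11 (Data Management): "Categorical data will be summarized using frequency tables (frequencies and percent". Continuous data get the number of values, mean, SD, median, minimum and maximum. The one test in the section is a chi-square on proportions of successes, which concerns efficacy. The documents give no confidence interval, no upper limit for a harm rate and no harm rate regarded as tolerable.

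On size, Section 3.0 says "The study will continue until at least 68 warts and 68 molluscum are treated", that "Half the lesions will be treated with plasma and the other half with standard of care", and that "A single patient must have minimum of 1 clinically diagnosed lesion treated and maximum of 20 treated".

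**The concern.** The likely result for the rarer harms is no events. Section 2.0 cites small clinical studies without side effects and a paediatric wart series that saw none of the four harms named in Section 15.0. Section 15.0 says that no side effects are known to date. A frequency table would then show 0 events and 0%.

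That figure is the same whether 34 lesions or 3,400 were treated, and it does not tell a reader which harm rates the trial has ruled out. The small series behind the protocol already reported no events. What this trial can add, in children from 4 years of age, is a bound on the rate, and the plan does not ask for one.

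The unit of analysis is also open. The plan does not say whether a percent is per lesion or per child. Lesions in one child share skin type, operator and device session, so they are not independent observations of harm. If the unit is chosen after the data are seen, the apparent precision can change considerably.

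**Working it through.** **The plan's own figure.** There is none for safety precision. The stated sizes are 68 lesions per disease (Section 3.0), or 68 + 68 = 136, and a total of 150 (Section 6.0). The two do not agree. The 150 is also not reproduced by a three-category chi-square with the Section 6.0 proportions at 80% power and alpha 0.05: a one-sample test against equal thirds needs about 50, and a two-arm comparison needs 202 to 206 in total. The point here does not depend on 150, but I show the limit for it.

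**Inputs.** NTAP lesions per disease: 68 / 2 = 34, a minimum. Both diseases pooled: 2 × 34 = 68. If 150 units are split equally: 75.

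**Formula.** For 0 events in n independent units, the exact upper limit is 1 − 0.05^(1/n) (one-sided 95%) or 1 − 0.025^(1/n) (two-sided 95%, Clopper-Pearson).

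| NTAP units, 0 events | One-sided 95% | Two-sided 95% |
|---|---|---|
| 34 lesions, one disease | 8.4% | 10.3% |
| 68 lesions, pooled | 4.3% | 5.3% |
| 75, if 150 is the total | 3.9% | 4.8% |

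**Cross-check.** The chance of no event in 34 lesions is (1 − p)^34. It is 17.5% for p = 5%, 5.9% for p = 8% and 2.8% for p = 10%.

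**Clustering.** The documents give neither the mean number of lesions per child nor an intraclass correlation (ICC), so these are assumptions. With 4 NTAP lesions per child, the effective size is 34 / (1 + 3 × ICC):

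- ICC 0.1: 34 / 1.3 = 26.2, limits 10.8% (one-sided) and 13.2% (two-sided).
- ICC 0.5: 34 / 2.5 = 13.6, limits 19.8% and 23.8%.

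**Counting children instead.** The number of children behind 34 NTAP lesions is also not given. Assumed values:

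- 34 children (one NTAP lesion each): 8.4% and 10.3%.
- 17 children (two each): 16.2% and 19.5%.
- 10 children: 25.9% and 30.8%.

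These are limits on the rate per child, which is a different quantity from the rate per lesion. It is the one whose units are independent, and the one a parent would ask about.

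**The case against.** The best defence is that the safety summary is descriptive and adequate as such. Frequencies will come with denominators, so a reader can work out the limit. Tolerability is graded on about ten signs, some of them common, so the output will not be only zeros. The 34 is a minimum, and since the same device is used in both diseases, harms may reasonably be pooled, which halves the limit. If the 150 in Section 6.0 means children, the child-level limits would be nearer 4% to 5%, or lower if most children receive both treatments.

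Much of this stands. The pooled figure belongs beside the per-disease figure, and the child-level figures above are illustrations. It does not remove the point. A reader can derive a lesion-level limit from 0/n, but not a child-level one unless children are counted.

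Three stronger readings are tempting, and the documents do not support them:

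- A reader might infer that the plan will declare the device safe or painless. Section 3.0 only says that the data will be analysed to find out, and the statement that "NTAP will be an equally efficient and painless alternative to cryotherapy" is a hypothesis. Section 15.0 allows that side effects may occur.
- A reader might infer that pain is summarised by means alone, so that a minority of children with pain would be hidden. Section 11 also plans SD, median, minimum and maximum, and a high maximum would show such pain.
- A reader might infer that VAS scores will be pooled over sessions, which would weight the treatment needing more sessions. Nothing says so. Sections 1.0 and 15.0 speak of pain at each treatment, which points the other way.

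Nor do the documents call for a new pain endpoint such as the share of children scoring zero. Section 10.0 has standard-of-care lesions treated first, with about 1 minute between groups, so residual pain could distort such a measure.

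**Conclusion.** The concern holds for harms and tolerability grades, and is a cheap improvement. As written, Section 11 would report an unseen harm as 0% while a lesion-level rate of up to 8.4% (one-sided) or 10.3% (two-sided) per disease, or 4.3% and 5.3% with both diseases pooled, is not excluded.

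These figures rest on the planned minimum size, an equal split, zero events and independence of lesions. Independence is favourable to the trial, since up to 20 lesions may come from one child. How much wider the true limits are depends on the number of lesions per child and their correlation, which the documents do not give. The conclusion does not extend to the planned pain summary.

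**What to change.** Add to Section 11: for each named harm and each treatment, by disease and for both diseases pooled, report the number of children with the event and the number of children treated, with an exact (Clopper-Pearson) 95% confidence interval. Count a child under a treatment if at least one lesion received it, and once only in the pooled row. For the 0 to 3 grades, state beforehand which grades count as an event. Lesion-level frequencies can stay as a supplement.

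Then word the safety conclusion by the upper limit, for example: no scarring was seen in n children treated with NTAP, and rates above the upper limit are excluded at the stated confidence.

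This needs no further patients, visits or measurements, only a few lines of analysis text. The price is a safety statement less favourable than 0%.

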10.0 Study Design / Methods

- A chart review of patient the patient's medical record will be completed and the following information will be collected for research purposes: DOB, demographics, contact information and diagnosis.
- Skin irritants, emollients, topical medications and other topical products cannot be applied to the study area 4 weeks prior to the start of the study and throughout the duration of the study. Details of what can and cannot be used can be discussed any time.
- During a clinical care visit, if a patient is eligible and agrees to participate, lesions will be selected by the dermatologist prior to procedure. The lesions will be marked randomly for a certain treatment regimen and photographs will be taken before each treatment and after completion of the study. Identifiers will be covered to protect identity. All images will be saved on a MUSC network secure box drive using a subject study number.
- The number of lesions treated will not exceed SOC recommendations. They will be determined by provider assessment and anatomical location.
- Participants with one lesion will receive either NTAP or standard of care (SOC). SOC is

Page 8 of 13

cryotherapy for warts and cantharidin for molluscum. Participants with greater than 2 lesions will receive equal treatment of NTAP and SOC. The number of lesions treated will be based off the providers assessment and anatomical location. Treatment of a single lesion or an odd number of multiple lesions will be based off a randomized list.

- All SOC lesions will be treated first to reduce the number of patients not wanting return to the more painful modality.
- All people in the room will be provided eye shields that must be worn during treatment. The patient will be placed in a comfortable position before the lesion is cleaned with alcohol.
- Each lesion will be treated for 1-2 minutes. Total treatment duration will be no longer than 20 minutes.
- The interval between treatment groups will about 1 minute.
- There will be a follow-up phone call a week after treatment to check on resolution and report any adverse events. If an adverse event is reported the study team members will access if the patient needs to be seen by a provider that day.

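### The only planned test, a chi-square, treats lesions as independent although one child may contribute 1 to 20, so its 5% error rate is not assured

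*Combined protocol and SAP*

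**What the plan says.** Section 11 (Data Management) lists descriptive summaries and one inferential method: "Chi-square analysis comparing the proportions of successes (equal chance outcomes". It names no unit of analysis, pairing, stratum or cluster.

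The design works at lesion level:
- Section 3.0 sets the recruitment target in lesions: "The study will continue until at least 68 warts and 68 molluscum are treated". It allocates them as lesions: "Half the lesions will be treated with plasma and the other half with standard of care".
- Section 3.0 gives the range per child: "A single patient must have minimum of 1 clinically diagnosed lesion treated and maximum of 20 treated". It adds a limit without a number: "Each patient will not have more lesions treated than SOC recommendations".
- Section 10.0 randomises lesions: "The lesions will be marked randomly for a certain treatment regimen". For children with several it says: "Participants with greater than 2 lesions will receive equal treatment of NTAP and SOC". A child with one lesion gets one treatment. A single lesion, or an odd number of several, is settled by a randomised list.

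Section 6.0 gives the size: "Total of 150 would be required (half control, half NTP) to achieve 80% power with an alpha of" .05. It uses three outcome proportions, has no term for clustering, and does not say in that sentence whether the 150 are lesions or participants. No section gives an expected number of lesions per child or an intraclass correlation.

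**The concern.** An ordinary chi-square takes its variance from independent observations. Lesions on one child share host immunity, skin and aftercare, so their outcomes can be correlated. The data will also mix within-child comparisons (several lesions, both treatments) with between-child comparisons (one lesion each). The planned test ignores both features.

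The error can go either way. If children differ only in how readily their lesions clear, an equal split within the child cancels that difference. The chi-square then overstates its variance and rejects too rarely. If the NTAP-versus-SOC difference itself varies between children, and a few children supply many lesions, the chi-square understates the variance and rejects too often. At stake is whether the p-value from the trial's only test means what it says.

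**Working it through.** **1. The plan's own figure, assuming independent lesions.** Inputs from section 6.0: null proportions 1/3 each; alternative 9/17, 3/17, 5/17; alpha 0.05; total 150. The 5% critical value on 2 df is 5.991.

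- One-sample test against thirds: w² = Σ(p₁ − p₀)²/p₀ = 0.194. This needs 50 lesions for 80% power.
- Two-arm 2×3 test, taking the thirds as the control arm (an assumption; section 6.0 calls them the null): w² = ½Σ[(p₁ − p̄)² + (p₀ − p̄)²]/p̄ = 0.0476. Noncentrality is 150 × 0.04764 = 7.15, power 66.5%. For 136 lesions (68 + 68) it is 6.48, power 61.9%. For 80% power, 203 are needed.

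Neither calculation yields 150. The two-arm shortfall exists before any clustering.

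**2. Direction of the error.** Take a latent normal outcome with total variance 1, child variance Vc, treatment-by-child variance Vt, and m lesions per child split equally. The shared child effect cancels in the difference, so

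true variance / variance assumed by chi-square = 1 − Vc + (m/2 − 1)Vt.

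This equals 1 at m = 2(1 + Vc/Vt). With Vc = 0.3 the turning point is 2(1 + 6) = 14 lesions per child at Vt = 0.05, 2(1 + 3) = 8 at 0.10, 2(1 + 1.5) = 5 at 0.20, and 2(1 + 1) = 4 at 0.30. Below it the test is conservative and above it liberal. The formula is approximate for three categories; the sizes below come from simulation.

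**3. Simulated type I error of the two-arm 2×3 chi-square, nominal 5%.** 10,000 runs per cell, 68 to 80 lesions (about one condition), proportions 9/17, 3/17, 5/17 in both arms. All variances and layouts are assumptions.

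| Children × lesions | Shared effect only (Vc 0.3-0.5) | Vc 0.3, Vt 0.05-0.10 | Vc 0.3, Vt 0.20-0.30 |
|---|---|---|---|
| 34 × 2 | 2.4-4.3% | 3-4% | about 3.5% |
| 17 × 4 | 2.4-4.3% | 3-4% | 5-6% |
| mixed: 12×1, 6×2, 6×4, 2×10 | 2.4-4.3% | 4-5% | 6-7% |
| 7 × 10 | 2.4-4.3% | 5-7% | 10-14% |
| 4 × 20 | 2.4-4.3% | 7-11% | 19-28% |

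The second column is the range over all multi-lesion layouts. With 68 single-lesion children the error is about 5%.

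**4. Two other readings, shared child effect only.**
- All lesions of a child get one treatment (68 lesions, thirds in both arms, latent correlation 0.3-0.6): 7.7-10.4% with 2 lesions per child, 12.2-22.5% with 4.
- The words about equal chance mean a one-arm test against thirds (latent correlation 0.3-0.5): 5-5.5% at 34 × 2, 7-10% at 17 × 4, 14-21% at 7 × 10, 25-39% at 4 × 20.

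**5. Power of a child-level analysis.** Complete clearance 53% (section 6.0) against an assumed 30%, shared effect only (Vc 0.3-0.5). A paired t-test on within-child differences stands in for a small-sample-corrected clustered analysis.

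| Layout | Chi-square | Child-level |
|---|---|---|
| 34 × 2 and 17 × 4 | 48-50% | about 55-60% |
| 7 × 10 | 49-50% | 46-50% |
| 4 × 20 | about 59% | 30-33% |

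**The case against.** Four points on the other side carry weight.

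- **The practical size is unknown.** Sections 3.0 and 10.0 limit lesions by standard of care and provider judgement. With modest effect variation (Vt 0.05-0.10, Vc 0.3), the two-arm error stays at 3-7% up to 10 lesions per child. This stands. A reader might infer that the chi-square necessarily inflates false positives; the documents do not support that. Clear inflation in the two-arm test with an equal split needs many lesions per child and varying effects together.
- **Power.** A reader might infer that clustering is why 80% is not reached. Step 1 shows otherwise: the two-arm figure on section 6.0's proportions is already about 66%. Clustering adds uncertainty but is not the main cause.
- **The remedy is not uniformly better.** A reader might infer that the chi-square simply wastes power. That is so with many children and few lesions each, but not at 7 × 10, and at 4 × 20 the child-level analysis has much lower power. The corrected GEE is also not exact: its error ran from 1.7% to 5.9% over the layouts simulated.
- **The layouts are idealised.** All multi-lesion layouts have even counts and an equal split, whereas section 10.0 expects odd counts too. Its equal-split rule covers more than 2 lesions, so the split at 34 × 2 is an assumption. Stratification by condition was not simulated.

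None of this supplies the missing link between lesion and child. A matched or stratified chi-square could have been meant, but section 11 does not say so.

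**Conclusion.** The concern holds for the type I error. The one planned test assumes an independence that the design does not provide, so 5% is not assured. That omission is certain; its size is not, because the documents give neither lesion counts per child nor variances. Under the assumptions shown, the two-arm test runs at about 2-4% with an equal split and a shared child effect only. It reaches about 13% (7 × 10) and 26% (4 × 20) with 30% treatment-by-child variance. It is also liberal if a child's lesions all receive one treatment, or if a one-arm test against thirds is meant. With almost all children contributing one lesion, it is sound.

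The unsupported 80% power is a separate defect, which a clustered analysis alone will not cure. This should be fixed, chiefly because the method can be settled cheaply before outcomes are seen.

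**What to change.** In section 11:

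1. Name the lesion as the unit of outcome and the participant as the cluster.
2. Replace the chi-square by a comparison of NTAP with SOC, stratified by condition, that accounts for the participant. Options:
   - a GEE with small-sample-corrected, child-level robust variance;
   - a mixed model with a random intercept and a random treatment effect by child (not simulated here);
   - a child-stratified Mantel-Haenszel or within-child permutation test, if the null is written as no effect in any child. Mantel-Haenszel held 4.0-5.2% under that null, but as a test of the average effect it gave 7-10% at 7 × 10 with Vt 0.05-0.10.
3. Rule out an uncorrected sandwich variance with few children: it gave 9-12% with 7 to 11 children and 18-19% with 4.
4. Report participants and lesions per participant with each result.

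In section 6.0, state whether the 150 are lesions or participants. Restate the power for the chosen analysis under an assumed lesion distribution, beside the figure for independent lesions on the same proportions.

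Cost: analysis wording, some programming and a new power calculation. No new data are needed, since section 10.0 already files images under a subject study number. The plan should state the downside: power rises with many children and few lesions each, does not rise at 7 × 10, and is clearly lower if very few children supply the lesions.

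### The only stated null is one third per response grade; no NTAP-versus-standard-of-care null or estimate is given, so the sole planned test, read with Section 6, does not address the comparative hypothesis

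*Combined protocol and SAP*

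**What the plan says.** Section 1.0 (Objectives / Specific Aims) sets a comparative hypothesis: "NTAP will be an equally efficient and painless alternative to cryotherapy for the treatment of molluscum and warts". Section 3.0 assigns half the lesions to plasma and half to SOC, which is cryotherapy for warts and cantharidin for molluscum. The endpoints section grades response as none, partial or complete, judged by a blinded assessor.

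Section 6.0 (Number of Subjects) gives the only null hypothesis: "Assumption for Probabilities for the Null hypotheses is P1=P2=P3=1, hence P1 = .333333, P2 = .333333, P3 = .333333", glossed as "or that each proportion has an equal chance". The alternative is a single distribution from an earlier plasma paper: "P1=9/17 (Full Resolution = .53), P2=3/17=.18 (Some Improvement), and P3=5/17=.29 (no improvement". The three P's are therefore response grades, not treatment arms. The resulting size is stated as "Total of 150 would be required (half control, half NTP) to achieve 80% power with an alpha of" .05.

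Section 11 (Data Management) lists descriptive summaries and one test: "Chi-square analysis comparing the proportions of successes (equal chance outcomes". It names no arms, table layout, time point or disease. The document gives no SOC response rate, no null of equal response under NTAP and SOC, and no equivalence or non-inferiority margin.

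**The concern.** The parenthesis in Section 11 repeats the wording of the Section 6 null. Taken together, the two sections describe a goodness-of-fit test of whether the three grades are equally likely. That test makes no use of the comparator. Nor is one third per grade a no-effect value: nothing in the document says that untreated, inertly treated or SOC-treated lesions divide that way.

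A test against one third can be significant when the two treatments perform identically, and non-significant when they differ. If the analyst follows the text, the trial's only p-value will not bear on its hypothesis. This does not depend on sample size, so more lesions would not cure it.

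**Working it through.** **Inputs.** Null: 1/3 per grade (Section 6). Alternative, reused here as the common true split: 9/17, 3/17, 5/17 (Section 6). Alpha 0.05. Two sample sizes per arm: 34, half of the 68 lesions per disease in Section 3.0; and 75, half of the 150 in Section 6. Assumptions: each unit is one lesion, lesions are independent, and the one-third test is applied to one arm (the documents do not say where it is applied).

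**Step 1: the plan's own figure.** For a goodness-of-fit chi-square with 2 degrees of freedom,

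w² = Σ(p − 1/3)² ÷ (1/3) = 3 × [(10/51)² + (−8/51)² + (−2/51)²] = 3 × 168/2601 = 0.1938.

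Power is the probability that a non-central chi-square (2 df, λ = n × w²) exceeds 5.991.

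| n | λ | Power |
|---|---|---|
| 34 | 6.59 | 0.627 |
| 50 | 9.69 | 0.802 |
| 75 | 14.53 | 0.937 |
| 150 | 29.07 | 0.999 |

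The written null and alternative reach 80% power at about 50 (51 with the rounded rates .53, .18, .29). The stated 150 is not reproduced.

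**Step 2: identical arms.** Let NTAP and SOC both follow 9/17, 3/17, 5/17. The correct answer to the comparative question is then no difference. The one-third test on one arm rejects with the probabilities in Step 1: about 63% at 34 lesions and 94% at 75. Simulation (40,000 runs) agrees. A 2×3 chi-square of NTAP against SOC on the same data rejects about 5% of the time at both sizes, as it should.

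**Step 3: illustrations only.** The splits below (complete/partial/none, in percent) are assumed and do not appear in the documents. Results are simulated.

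| Assumed truth | One-third test | Two-arm chi-square |
|---|---|---|
| Nearly inert treatment, 2/5/93 | rejects about 100% | not applicable |
| NTAP one third per grade, SOC 10/20/70 | rejects about 5% (NTAP arm) | rejects 84% (34 per arm), 99% (75 per arm) |

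The second row is deliberately extreme, because it puts NTAP exactly on the null. It shows that the test can stay silent in the face of a large difference.

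**Step 4: what a between-arm test would need.** If SOC is assumed, for illustration, to be one third per grade and NTAP follows the pilot split, a 2×3 chi-square needs about 203 lesions in total for 80% power. At 150 its power is about 66%. For non-inferiority on complete resolution, with both rates assumed to be 9/17 and one-sided alpha 0.025, the totals are 784, 348 and 196 for assumed margins of 10, 15 and 20 percentage points.

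**The case against.** The best reply is that Section 11 speaks of comparing proportions of successes, in a trial with two randomised treatments and a sample size divided between control and plasma. An ordinary NTAP-versus-SOC comparison may be what the authors have in mind. The sample size does not fit the goodness-of-fit reading neatly either: that test needs about 50, not 150 in two halves. One two-arm calculation does give exactly 150: 0.33 against 0.53, one-sided 0.05, 75 per arm.

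Part of this stands. The line is ambiguous, and a reader might infer that the sponsor has definitely committed to a one-sample test and will never compare the arms. The documents do not support that; they leave the comparison unstated. A reader might also infer that 150 arose as 3 × 50. The arithmetic matches, but nothing in the text shows it.

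The reply does not remove the problem. The two-arm route to 150 needs a one-sided test and an SOC clearance rate of 0.33, neither of which is stated; with 1/3 in place of 0.33 it gives 156. The parenthesis in Section 11 echoes the Section 6 null, and no other null appears. Even on the charitable reading, the sole test lacks arms, a null, a time point and a disease stratum.

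A further fair point is that an ordinary two-arm chi-square would not be a full remedy. Failing to reject does not show equal efficacy. With SOC assumed at 70/15/15 and NTAP at the pilot split, NTAP clears about 17 points fewer lesions (70% against 53%), yet that test fails to reject about 73% of the time at 34 per arm and 45% at 75. It also ignores that one patient may contribute up to 20 lesions, with both treatments when there are several.

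**Conclusion.** The point holds in this form: the only null written down is one third per grade, the sole test repeats it, and no null, estimate or margin comparing NTAP with SOC is stated although the hypothesis is comparative. Read with Section 6, the test does not answer the trial's question.

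The firm measure of size is the identical-arms case, which uses the protocol's own pilot figures: 63% or 94% rejection where a between-arm test gives about 5%. It rests on independent lesions and on the one-third test being applied to a single arm. The cases in Step 3 and the sample sizes in Step 4 rest on response rates or margins that the documents do not give, and should be read as illustrations. In particular, they do not establish that the trial enrols too few lesions: without an SOC rate and a margin, that cannot be judged.

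**What to change.** **Section 11.** Delete the parenthesis about equal chance. Make the main analysis the NTAP-minus-SOC difference in complete resolution on the blinded grade, within each disease, at a named time point, with a 95% CI. The method should allow for several lesions, and both treatments, in the same patient; GEE or a mixed model clustered on patient would do. Test neither arm against one third. State that a non-significant difference will not be taken as showing equal efficacy, and that any such claim will rest on the CI read against a margin the sponsor sets in advance.

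**Section 6.** Replace the one-third null with the between-arm comparison. Restate the power or precision that the planned number of lesions gives, showing the assumed SOC rate, because 150 does not follow from the null and alternative now written.

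**Cost.** A few sentences, a slightly more complex analysis, and a restated power figure that will probably be less favourable. No extra patients or data are required.
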